10.2.1 Adverse device effects

Adverse events are recorded at the AE CRF page at the time when they occur. If an adverse event is related to the device by assessment of the investigator it is counted as an adverse device event.

[...]

Additional planned summaries include overall ADEs and SADEs. Summaries to be presented include:

- Incidence of TEADEs – Overview
- Incidence of TEADEs by SOC, HLT, and PT
- Incidence of serious TEADEs by SOC, HLT, and PT
- Incidence of TEADEs leading to death
- Incidence of TEADEs leading to discontinuation
- **Incidence of non-TEADEs (only listed and not summarized in a table)**

For definition of serious, unanticipated and unanticipated serious ADEs (USADEs) see protocol of DV0004.

Adverse device effects which started before Week 4 and were ongoing at the data cut off will be included with the status remaining as ongoing. Adverse device effects which were ongoing at Week 4 but with an end date before the data cut off will be included with their end date as recorded.

10.2.2 Injection site reaction

Injection site reactions are recorded at the AE CRF page at the time when they occur. All AEs will be coded and classified by system organ class, high level term, and preferred term. An AE with High Level Terms of “Administration site reactions NEC” and “Injection site reactions” will be evaluated as injection site reaction.

All injection site reactions for self-injection with a start date on or following the first self-administration of study treatment through the final self-administration of study treatment + 7 days will be listed.

13.2 SAP Amendment 2

Rational for the amendment

Details regarding the handling of COVID-19 pandemic data have been added to the SAP. The summaries for the PK data have been updated following discussions in the Data Evaluation Meeting (#2). A sensitivity analysis for the SIAQ data has been added following DEM2.

Modifications and changes

Global changes

The following changes were made throughout the SAP:

- The addition of clarification of which outputs are to be presented to assess the impact of COVID-19 pandemic.
- Sections have been renumbered to account for new COVID-related sections. These will not be individually noted.

Specific changes

Change #1

Text added at the end of Section.

Section 3.3 Protocol deviations

[..] Following the declaration of the global COVID-19 pandemic by the World Health Organization in March 2020, protocol deviations will be identified as “related to COVID-19” where applicable.

Change #2

Subsection added for Section 3.8 Changes to protocol-defined analyses.

Section 3.8.1 Changes related to COVID-19

The impact of the COVID-19 pandemic on study procedures and/or conduct and on the primary safety endpoints (TEADEs, serious TEADEs, and study withdrawal due to TEADEs) will be investigated and additional outputs provided as appropriate. These analyses were not planned as part of the protocol as the pandemic scale was unprecedented.

The additional analyses are described in the following sections of the SAP:

- Subject disposition, including details of impacted visits and effects on collection and reporting of efficacy data (Section 5.1.1)
- Protocol deviations potentially related to COVID-19 (Section 5.2)
- Impact of COVID-19 on study (Section 5.3)
- Demographics, baseline characteristics (Sections 6.1 and 6.2)
- Adverse events (Section 10.2.2)
- Primary outcome variable (Section 11.1)

Change #3

Subsection added to Section 4.9 Additional study-specific information.

Section 4.9.1 COVID-19 category definition

The coronavirus disease of 2019 (COVID-19) pandemic was declared by the WHO on 11 March 2020. The worldwide pandemic restricted travel and had potential impact on ongoing clinical trials. The following definitions will be used to present pre-specified summaries:

- *Pre-pandemic*: Events or assessments occurring before 11-Mar-2020
- *During pandemic*: Events or assessments occurring on or after 11-Mar-2020

A post-pandemic definition is not applicable to this short study.

Change #4

Subsection added to Section 5.1 Subject disposition.

Section 5.1.1 Impact of COVID-19 on subject disposition

Subject disposition will also be summarized by COVID-19 enrollment period (pre- and during-pandemic), as defined in Section 4.9.1. The number of completed, missed and partial visits will be presented by COVID-19 enrollment period.

Change #5

Section 5.2 Protocol deviations

A summary of number and percentage of subjects with an important protocol deviation (including a summary of subjects excluded from any analysis set due to important protocol deviations) by DV0004 device group will be provided for the SS-s and SS-a.

A by-subject listing of important protocol deviations will be provided.

Has been changed to

A summary of number and percentage of subjects with an important protocol deviation (including a summary of subjects excluded from any analysis set due to important protocol deviations) by DV0004 device group will be provided for the SS-s and SS-a. **A summary of COVID-19 related important device protocol deviations will be presented by visit for the SS-s and SS-a. COVID-19 related important protocol deviations will be identified by the prefix of “COVID” in the deviation verbatim text.**

By-subject listings of important protocol deviations **and COVID-related important device protocol deviations** will be provided separately.

Change #6

Section added:

Section 5.3 Impact of COVID-19

The impact of the COVID-19 pandemic on study procedures and conduct, such as missed/remote visits, interruption of study treatment, will be documented using the information collected on a

dedicated eCRF page. The number and percentage of subjects impacted by COVID-19 will be presented overall and by country.

A by-subject listing of the impact of COVID-19 on study visits will be provided.

Change #7

Text added to section.

9.1 Pharmacokinetics

PK samples at DV0004 baseline will be summarized under administration by site personnel (since the previous dose was given by site personnel). PK samples associated with self-administration (at Week 4 and Week 8), but where the previous injection was done by site personnel or care-giver, will be listed but not be used for summary statistics.

Only pre-dose (trough) concentrations will be included while summarizing tables and figures. If the dosing for a visit is +/- 7 days out of window, then the plasma concentration from that visit will be excluded from the PK summary. **PK samples are expected to be collected prior to dosing. PK samples collected >14 days after the preceding dose and no later than 1 hour after the current dose will be included in the summary.** PK samples collected later than 1 hour after dosing will be excluded from summary statistics. **PK results at visits following a previous non-dosing visit will be excluded from summary statistics.**

[...]

Boxplots of plasma concentration will be presented by visit, by device presentation, and by cumulative ADA_b status. Cumulative ADA_b status is defined in Section 9.2. **Boxplots of plasma concentration will be presented by visit, by device presentation and by injection site, and by BMI tertile.**

All PK results will be listed. Baseline PK samples are the PK samples prior to first dose of Bimekizumab at DV0004 entry visit.

In addition, the PK results from all subjects not in PK-PPS-s or PK-PPS-a will be listed based on the SS-a and SS-s. **All concentrations will be listed as received, prior to any substitution of BLQ and LLOQ values. The listing will include flags for concentration that were excluded from the summary statistics, with the reason for exclusion.**

Change #8

Section 9.2 “Pharmacodynamics and Immunogenicity” renamed to “Immunogenicity”.

[..]

If a sample is collected within 7 days (inclusive) before or after the visit date at which the drug was administered, the ADA_b results for that sample will be associated with the scheduled visit and summarized accordingly. Samples collected outside this window and all subsequent samples for that subject will be excluded from the ADA_b summaries and figures and will be listed only.

[..]

Cumulative ADA_b status is used for the box plots described in Section 9.1. Cumulative ADA_b status is derived as follows:

- If a subject is ADA b positive at any time up to and including the respective visit, they are assigned ADA b cumulative positive status for that and all subsequent visits.
- Otherwise, the subject remains negative at that respective visit and assigned ADA b cumulative negative.

Has changed to

[..]

If a sample is collected within **21** days (inclusive) before or after the visit date at which the drug was administered, the ADA b results for that sample will be associated with the scheduled visit and summarized accordingly. Samples collected outside this window and all subsequent samples for that subject will be excluded from the by-visit ADA b summaries and figures and will be listed only. **This window will not apply to the summary of cumulative ADA b status, all available data will be used to derive the cumulative ADA b status.**

[..]

Cumulative ADA b status is used for the box plots described in Section 9.1. Cumulative ADA b status is derived as follows:

a. Considering data in DV0004 only:

- If a subject is ADA b positive at any time **during DV0004** up to and including the respective DV0004 visit, they are assigned ADA b cumulative positive status for that and all subsequent visits. **This will be based on the confirmatory assay at each visit in DV0004 (Baseline, Week 4, Week 8).**
- Otherwise, the subject remains negative at that respective **DV0004** visit and assigned ADA b cumulative negative.

b. Considering data in the feeder studies (PA0010, PA00011) and DV0004:

- **If a subject is ADA b positive at any time in PA0010/PA0011 and DV0004 up to and including the respective DV0004 visit, they are assigned ADA b cumulative positive status for that and all subsequent visits. This will be based on the cumulative status at DV0004 Entry Visit (last visit in Feeder Study) and the confirmatory assay results in DV0004 (Week 4 and Week 8).**
- **Otherwise, the subject remains negative at that respective DV0004 visit and assigned ADA b cumulative negative.**

Change #9

Subsection 10.2.2 Impact of COVID-19 on adverse events added.

Section 10.2.2 Impact of COVID-19 on adverse events

In order to assess the impact of the COVID-19 global pandemic on the primary safety endpoint of incidence of TEADEs and serious TEADEs, additional summaries will be presented. Summaries of TEADEs and Serious TEADEs will be presented by COVID-19 enrollment period

and timing of the ADE relative to the WHO declared COVID-19 pandemic (enrolled prior to pandemic – ADE prior to pandemic, enrolled prior to pandemic – ADE during pandemic, enrolled during pandemic– ADE during pandemic), as defined in Section 4.9.1. ADEs leading to discontinuation will be presented by COVID-19 enrollment period and timing of ADE relative to the pandemic period as well.

For reporting purposes, AEs will be assigned to ‘Prior to COVID-19 pandemic’ or ‘During the COVID-19 pandemic’ based on the following:

- If the date of AE or ADE onset (based on imputed start date) is prior to 11 March 2020 the AE/ADE will be assigned as ‘Prior to COVID-19 pandemic’
- If the date of AE or ADE onset (based on imputed start date) is on or after 11 March 2020 the AE/ADE will be assigned as ‘During the COVID-19 pandemic’

A ‘Post the COVID-19 pandemic’ phase will not be assigned for AE reporting as the pandemic is expected to be ongoing at the time of last subject last visit.

[..]

13.3 SAP Amendment 3

Rational for the amendment

An additional set of analyses for the SIAQ and VAS data has been added following data cleaning. The details for this analysis have been added to the SAP text in Section 11.3.1, Section 11.3.2 and Section 11.3.3.

Modifications and changes

Specific changes

Change #1

Clarification added to the derivation of the subscale scores when missing data occurs.

Section 9.1 Pharmacokinetics

[...]

PK summaries will be based on observed values. No imputation will be used. However, if plasma concentration measurements are below the level of quantification, then for calculation of the derived statistics the result will be set to $\frac{1}{2}$ of the lower level of quantification (LLOQ). Descriptive statistics including the geometric mean, geometric coefficient of variation, and geometric mean 95% confidence interval (CI) if applicable will be calculated if at least $\frac{2}{3}$ of the values of interest are above the LLOQ. If this is not the case, only median, minimum, and maximum will be presented. Time from previous bimekizumab dose to DV0004 visit will be summarized by device presentation.

Has changed to

[...]

PK summaries will be based on observed values. No imputation will be used. However, if plasma concentration measurements are below the level of quantification, then for calculation of the derived statistics the result will be set to $\frac{1}{2}$ of the lower level of quantification (LLOQ). Descriptive statistics including the geometric mean, geometric coefficient of variation, and geometric mean 95% confidence interval (CI) if applicable will be calculated if at least $\frac{2}{3}$ of the values of interest are above the LLOQ. If this is not the case, only median, minimum, and maximum will be presented. Time from previous bimekizumab dose to DV0004 visit will be summarized by device presentation.

A minimum of 3 values are required to calculate summary statistics. If only 2 values are available, then these should be presented as the minimum and maximum with other descriptive statistics reported as missing

Change #2

Clarification added to the derivation of the subscale scores when missing data occurs.

Section 11.3.1 Pre-injection SIAQ (versions 2.0 and 2.1)

[...]

In the case of missing values, no subscale score will be calculated if more than 50% of the items within the subscale are missing.

Has changed to

[...]

In the case of missing values, no subscale score will be calculated if more than 50% of the items within the subscale are missing. **The subscale scores will be calculated out of the non-missing individual transformed item scores.**

Change #3

Subsection 11.3.1.1 has been added.

Section 11.3.1.1 Additional Analysis for Pre-injection SIAQ

There will be an additional analysis to present the summary described in Section 11.3.1 for the subgroup of subjects who completed both the pre-injection SIAQ and the post-injection SIAQ per protocol. The subgroup will include subjects who completed the pre-injection SIAQ and post-injection SIAQ correctly in relation to injection administration, and also completed the correct version of the questionnaire assigned based on the device group. A pre-injection SIAQ is considered to be impacted if it is administered after self-injection. Summary statistics for all individual items and each subscale score will be produced for DV0004 Baseline.

Change #4

Clarification added to the derivation of Ease of Use subscale and the derivation of the subscale scores when missing data occurs.

Section 11.3.2 Post-injection SIAQ (versions 2.0 and 2.1)

[...]

In the case of missing values, no subscale score will be calculated if more than 50% of the items within the subscale are missing.

[...]

Has changed to

[...]

In the case of missing values, no subscale score will be calculated if more than 50% of the items within the subscale are missing. **The subscale scores will be calculated out of the non-missing individual transformed item scores. If a subject completed the incorrect version of the questionnaire (for example, a subject randomized to bimekizumab-SS-1mL and completed version 2.1 of the post-injection SIAQ), then Q11 will be excluded from the derivation of Ease of Use subscale.**

[...]

Change #5

Subsection 11.3.2.1 has been added.

Section 11.3.2.1 Additional Analysis for Post-injection SIAQ

There will be an additional analysis performed for post-injection SIAQ. It will repeat the analysis described in Section 11.3.2 only including the subgroup of subjects who completed both the pre-injection SIAQ and the post-injection SIAQ correctly as described in the protocol. A post-injection questionnaire is considered to be impacted if it is administered before self-injection, or longer than 30 minutes after self-injection, or if the incorrect post-injection SIAQ version has been administered for the randomized device group. Version 2.0 of the SIAQ will be used to assess bimekizumab-SS-1mL and version 2.1 of the SIAQ will be used to assess bimekizumab-AI-1mL. Subjects who have an impacted pre- or post-injection SIAQ at any visit will be excluded from the summary. Note that subjects complete both pre- and post-injection questionnaires at Baseline, and only post-injection SIAQ at Week 4. Summary statistics for all individual items and each subscale score will be produced for DV0004 Baseline and Week 4.

Change #6

Subsection 11.3.3.1 has been added.

Section 11.3.3.1 Additional Analysis for Injection site pain

There will be an additional analysis of the summary described in Section 11.3.3 limited to subjects who correctly completed the visual analog scale of injection site pain after the injection at both visits. Summary statistics of actual values at DV0004 Baseline and Week 4 and change from DV0004 Baseline values will be used to summarize injection site pain by visit after self-injection.

13.4 SAP Amendment 4

Rational for the amendment

Aligning the immunogenicity text to use the terminology for ADA_b samples consistent with the BKZ program. No change to analyses, administrative change.

Specific Changes

Change #1

Section 9.1 Pharmacokinetics

[...]

Boxplots of plasma concentration will be presented by visit, by device presentation, and by cumulative ADA_b status. Cumulative ADA_b status is defined in Section 9.2. Boxplots of plasma concentration will be presented by visit, by device presentation and by injection site, and by BMI tertile.

[...]

Has been updated to

[...]

Boxplots **and summaries** of plasma concentration will be presented by visit, by device presentation, and by cumulative ADA_b status **considering DV0004 alone and considering DV0004 and the feeder studies (see Section 9.2)**. Cumulative ADA_b status is defined in Section 9.2. Boxplots **and summaries** of plasma concentration will be presented by visit, by device presentation and by injection site, and by BMI tertile.

[...]

Change #2

Section 9.2 Immunogenicity

The immunological variable is anti-bimekizumab antibodies (ADA_b) evaluated at DV0004 Baseline and Week 4, and PA0012 Week 8 visits. To allow for an analysis of ADA_b, blood samples will be taken before self-injection at the DV0004 Baseline Visit and DV0004 Week 4 (Visit 2), and before injection by site personnel at PA0012 Week 8 (Visit 3 of PA0012). ADA_b status at or prior to the PK sampling (at DV0004 Baseline, DV0004 Week 4, and PA0012 Week 8) will be used in the summaries.

ADA_b will be assessed using a tiered approach: screening, confirmatory, and titer assays will be used.

Samples will first be evaluated in the screening assay using a false positivity rate of 5% (reported as 'above the cut-point' ACP or 'below the cut-point' [BCP]), followed by analysis of screened positive samples (reported as ACP) in the confirmatory assay (which is a drug depletion assay) to confirm the true positivity of the samples (reported as either 'confirmed positive' [CP] or 'not confirmed positive' [NCP]). Samples that are CP will be evaluated in a titration assay to quantify the ADA_b level and will be reported as titer (reciprocal dilution factor including minimum required dilution [MRD]). Screening, confirmatory and titer cut points of the respective assays

will be determined by the bioanalytical laboratory which will report the bioanalytical result from the respective assays.

If a sample is collected within 21 days (inclusive) before or after the visit date at which the drug was administered, the ADA_b results for that sample will be associated with the scheduled visit and summarized accordingly. Samples collected outside this window will be excluded from the by-visit ADA_b summaries and figures and will be listed only. This window will not apply to the summary of cumulative ADA_b status, all available data will be used to derive the cumulative ADA_b status.

ADA_b status will be derived as follows:

- Samples that are either BCP or ACP and NCP will be defined as **ADA_b negative**.
- Sample values that are ACP and CP will be defined as **ADA_b positive** (regardless of whether or not a titer is available)

[...]

The number and percentage of ADA_b-positive and ADA_b-negative subjects before self-injection (DV0004 Baseline) and after self-injection (at DV0004 Week 4 and PA0012 Week 8) will be summarized by visit. The ADA_b visit status will be based on the confirmatory assay at the respective visit. This visit status will be used for the summary tables.

[...]

The number and percentage of ADA_b-positive and ADA_b-negative subjects before self-injection (DV0004 Baseline) and after self-injection (at DV0004 Week 4 and PA0012 Week 8) will be summarized by visit. The ADA_b visit status will be based on the confirmatory assay at the respective visit. This visit status and the overall status (considering data in DV0004 only and data in DV0004 and the feeder studies) will be used for the summary tables and will be based on the Safety Set.

Cumulative ADA_b status is used for the box plots and summaries described in Section 9.1.

Cumulative ADA_b status is derived as follows:

- a. Considering data in DV0004 only:
 - If a subject is ADA_b positive at any time during DV0004 up to and including the respective DV0004 visit, they are assigned ADA_b cumulative positive status for that and all subsequent visits. This will be based on the confirmatory assay at each visit in DV0004 (Baseline, Week 4, Week 8).
 - Otherwise, the subject remains negative at that respective DV0004 visit and assigned ADA_b cumulative negative.
- b. Considering data in the feeder studies (PA0010, PA00011) and DV0004:
 - If a subject is ADA_b positive at any time in PA0010/PA0011 and DV0004 up to and including the respective DV0004 visit, they are assigned ADA_b cumulative positive status for that and all subsequent visits. This will be based on the cumulative status at DV0004

Entry Visit (last visit in Feeder Study) and the confirmatory assay results in DV0004 (Week 4 and Week 8).

- Otherwise, the subject remains negative at that respective DV0004 visit and assigned ADA b cumulative negative.

Has been updated to

The immunological variable is anti-bimekizumab antibodies (ADAb) evaluated at DV0004 Baseline and Week 4, and PA0012 Week 8 visits. To allow for an analysis of ADAb, blood samples will be taken before self-injection at the DV0004 Baseline Visit and DV0004 Week 4 (Visit 2), and before injection by site personnel at PA0012 Week 8 (Visit 3 of PA0012). ADAb status at or prior to the PK sampling (at DV0004 Baseline, DV0004 Week 4, and PA0012 Week 8) will be used in the summaries.

~~ADAb will be assessed using a tiered approach: screening, confirmatory, and titer assays will be used.~~ **The ADAb will be assessed using a 3-tiered assay approach: Screening, confirmatory, and titration assays.**

~~Samples will first be evaluated in the screening assay using a false positivity rate of 5% (reported as ‘above the cut point’ ACP or ‘below the cut point’ [BCP]), followed by analysis of screened positive samples (reported as ACP) in the confirmatory assay (which is a drug depletion assay) to confirm the true positivity of the samples (reported as either ‘confirmed positive’ [CP] or ‘not confirmed positive’ [NCP]). Samples that are CP will be evaluated in a titration assay to quantify the ADAb level and will be reported as titer (reciprocal dilution factor including minimum required dilution [MRD]). Screening, confirmatory and titer cut points of the respective assays will be determined by the bioanalytical laboratory which will report the bioanalytical result from the respective assays.~~

The Screening cut point will be used to determine the ADAb status in the test sample as “Positive Screen” (PS) or “Negative Screen” (NS). For samples presenting anti-BKZ antibody levels that are PS, further confirmatory assay will be performed, and the result of which will be reported as either “Positive Immunodepletion” (PI) or “Negative Immunodepletion” (NI).

ADAb status for each visit will be derived as follows:

- **Samples that are either NS or PS and NI will be defined as ADAb negative.**
- **Sample values that are either NS or PS and NI and where the BKZ concentration exceeds the validated ADAb assay drug tolerance limit (200 µg/mL) will be defined as inconclusive.**
- **Sample values that are PS and PI will be defined as ADAb positive (regardless whether a titer is available or not)**
- **Missing if it does not go into one of the above categories.**

If a sample is collected within 21 days (inclusive) before or after the visit date at which the drug was administered, the ADA_b results for that sample will be associated with the scheduled visit and summarized accordingly. Samples collected outside this window will be excluded from the by-visit ADA_b summaries and figures and will be listed only. This window will not apply to the summary of cumulative ADA_b status, all available data will be used to derive the cumulative ADA_b status.

~~ADA_b status will be derived as follows:-~~

- ~~• Samples that are either BCP or ACP and NCP will be defined as **ADA_b negative**.~~
- ~~Sample values that are ACP and CP will be defined as **ADA_b positive** (regardless of whether or not a titer is available)~~

[...]

The number and percentage of ADA_b-positive and ADA_b-negative subjects before self-injection (DV0004 Baseline) and after self-injection (at DV0004 Week 4 and PA0012 Week 8) will be summarized by visit. The ADA_b visit status will be based on the confirmatory assay at the respective visit. This visit status **and the overall status (considering data in DV0004 only and data in DV0004 and the feeder studies)** will be used for the summary tables **and will be based on the Safety Set**.

[...]

The number and percentage of ADA_b-positive and ADA_b-negative subjects before self-injection (DV0004 Baseline) and after self-injection (at DV0004 Week 4 and PA0012 Week 8) will be summarized by visit. The ADA_b visit status will be based on the confirmatory assay at the respective visit. This visit status and the overall status (considering data in DV0004 only and data in DV0004 and the feeder studies) will be used for the summary tables and will be based on the Safety Set.

Cumulative ADA_b status is used for the box plots and summaries described in Section 9.1. Cumulative **and overall** ADA_b status is derived as follows:

a. Considering data in DV0004 only:

- If a subject is ADA_b positive at any time during DV0004 up to and including the respective DV0004 visit, they are assigned ADA_b cumulative positive status for that and all subsequent visits. This will be based on the confirmatory assay at each visit in DV0004 (Baseline, Week 4, Week 8).
- ~~Otherwise, the subject remains~~ **If a subject has only negative at that respective DV0004 visit and assigned ADA_b cumulative samples or only one missing/inconclusive sample with all negative ADA_b samples up to that timepoint, the subject will be classified as negative.**
- **Otherwise, the study participant will be classified in the missing ADA_b category.**

b. Considering data in the feeder studies (PA0010, PA0011) and DV0004:

- If a subject is ADA_b positive at any time in PA0010/PA0011 and DV0004 up to and including the respective DV0004 visit, they are assigned ADA_b cumulative positive status

for that and all subsequent visits. This will be based on the cumulative status at DV0004 Entry Visit (last visit in Feeder Study) and the confirmatory assay results in DV0004 (Week 4 and Week 8).

- ~~Otherwise, the subject remains~~ **If a subject has only negative at that respective DV0004 visit and assigned ADA b cumulative samples or only one missing/inconclusive sample with all negative ADA b samples up to that timepoint, the subject will be classified as negative.**
- **Otherwise, the study participant will be classified in the missing ADA b category.**

This document cannot be used to support any marketing authorization application and any extensions or variations thereof.

PUBLIC COPY

STATISTICAL ANALYSIS PLAN SIGNATURE PAGE

This document has been reviewed and approved per the Review and Approval of Clinical Documents Standard Operating Procedures. Signatures indicate that the final version of the Statistical Analysis Plan (SAP) or amended SAP is released for execution.

This document cannot be used to support any marketing authorization application and any extensions or variations thereof.

PUBLIC COPY

Approval Signatures

Name: dv0004-sap-amend-4
Version: 1.0
Document Number: CLIN-000182610
Title: dv0004-sap-amend-4
Approved Date: 16 Dec 2021

| Document Approvals | |
|-------------------------------|---------------------------------------------------------------------------------------------------------|
| Approval Verdict: Approved | Name: [REDACTED] Capacity: Subject Matter Expert Date of Signature: 16-Dec-2021 12:04:58 GMT+0000 |

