PK summaries will be based on observed values. No imputation will be used. However, if plasma concentration measurements are below the level of quantification, then for calculation of the derived statistics the result will be set to ½ of the lower level of quantification (LLOQ). Descriptive statistics including the geometric mean, geometric coefficient of variation, and geometric mean 95% confidence interval (CI) if applicable will be calculated if at least ⅓ of the values of interest are above the LLOQ. If this is not the case, only median, minimum, and maximum will be presented. Time from previous bimekizumab dose to DV0004 visit will be summarized by device presentation.

A minimum of 3 values are required to calculate summary statistics. If only 2 values are available, then these should be presented as the minimum and maximum with other descriptive statistics reported as missing.

Boxplots and summaries of plasma concentration will be presented by visit, by device presentation, and by cumulative ADA_b status considering DV0004 alone and considering DV0004 and the feeder studies (see Section 9.2). Cumulative ADA_b status is defined in Section 9.2. Boxplots and summaries of plasma concentration will be presented by visit, by device presentation and by injection site, and by BMI tertile.

All PK results will be listed. Baseline PK samples are the PK samples prior to first dose of Bimekizumab at DV0004 entry visit.

In addition, the PK results from all subjects not in PK-PPS-s or PK-PPS-a will be listed based on the SS-a and SS-s. All concentrations will be listed as received, prior to any substitution of BLQ and LLOQ values. The listing will include flags for concentration that were excluded from the summary statistics, with the reason for exclusion.

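### SAP 9.1 prints a geometric mean, geometric CV and 95% CI when only one-third of troughs are quantifiable, so up to two-thirds of a cell can be one substituted value (low severity)

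*SAP*

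**What the plan says.** SAP 9.1, in its current text, substitutes ½ LLOQ for every concentration below the limit before derived statistics are calculated. It then sets a gate: "Descriptive statistics including the geometric mean, geometric coefficient of variation, and geometric mean 95% confidence interval (CI) if applicable will be calculated" when at least ⅓ of the values of interest are above the LLOQ. When the gate is not met, the fallback is limited: "If this is not the case, only median, minimum, and maximum will be presented". The section also sets a floor on cell size: "A minimum of 3 values are required to calculate summary statistics".

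The same section asks for plasma concentration summaries by visit and device, split by cumulative ADAb status (under two definitions), by injection site and by BMI tertile. Neither 9.1 nor the list of PK statistics in SAP 3.1 asks for the number of values below LLOQ in a summary table.

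The sentence also appears in SAP Amendment 3 (Section 13.3, Change #1), where both the before and the after text say the statistics "will be calculated if at least $\frac{2}{3}$ of the values of interest are above the LLOQ". What that change added was the three-value minimum. Amendment 4 (Section 13.4) edits another sentence of 9.1 and describes itself as "No change to analyses, administrative change".

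**The concern.** A geometric mean and a t-interval on the log scale treat every entry as a measurement. Under the one-third gate, most entries in a cell may be the same number, fixed by the assay limit and not by the subject's exposure. When more than half are below LLOQ, the median is that number too, so it cannot serve as a check on the geometric mean beside it. A printed minimum of ½ LLOQ shows that at least one value was substituted, but not how many.

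Trough levels by device, injection site and BMI tertile are a stated objective. Two cells could differ because their substituted shares differ and not because exposure differs, and the summary table would not show it.

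**Working it through.** **Inputs.** Gate of one-third, substitution at ½ LLOQ and minimum of 3 values: SAP 9.1. Comparison gate of two-thirds: SAP 13.3. PK-evaluable subjects, 50 per arm and 16 to 17 per BMI tertile: SAP 2.4. The documents give no LLOQ, trough CV or below-LLOQ rate, so these are assumed below.

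**The plan's own figure.** 100/3 = 33.3 enrolled per tertile and 50/3 = 16.7 PK-evaluable per tertile. These match the stated 33 and 16 to 17.

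**Substituted values allowed (no assumption needed).** Largest number = n − ceil(gate × n).

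| n | one-third gate | two-thirds gate |
|---|---|---|
| 50 | 50 − 17 = 33 (66%) | 50 − 34 = 16 (32%) |
| 17 | 17 − 6 = 11 (65%) | 17 − 12 = 5 (29%) |
| 16 | 16 − 6 = 10 (62.5%) | 16 − 11 = 5 (31%) |
| 3 | 3 − 1 = 2 (67%) | 3 − 2 = 1 (33%) |

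In every entry of the one-third column, more than half the values are substituted, so the median is too. In the two-thirds column it is always a measured value.

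**Bias of the geometric mean (lognormal assumed).** Let the true log mean be 0, s = √ln(1 + CV²), q the quantifiable share, z = Φ⁻¹(1 − q) and L = s·z the log LLOQ. The expected log value after substitution is (1 − q)(L − ln 2) + s·φ(z). At q = 0.5, z = 0 and L = 0, which leaves 0.3989·s − 0.3466.

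- CV 30%: s = 0.2936; 0.1171 − 0.3466 = −0.2295; ratio to truth 0.795.
- CV 50%: s = 0.4724; 0.1884 − 0.3466 = −0.1581; ratio 0.854.
- CV 100%: s = 0.8326; 0.3321 − 0.3466 = −0.0145; ratio 0.986.
- CV 200%: s = 1.2686; 0.5061 − 0.3466 = +0.1595; ratio 1.173.

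The direction of the bias depends on the CV, so a reader cannot correct for it.

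**Coverage of the 95% CI, with the gate applied.** These come from simulation with at least 20,000 datasets per setting, at q = 0.5, keeping only datasets that pass the one-third gate (about 90% at n=16 and 99% at n=50).

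| CV | geometric mean/truth, n=16 | coverage, n=16 | geometric mean/truth, n=50 | coverage, n=50 |
|---|---|---|---|---|
| 30% | 0.81 | 66–67% | 0.80 | 9–10% |
| 50% | 0.88 | 89% | 0.86 | 53% |
| 100% | 1.02 | 98% | 0.99 | 95% |
| 200% | 1.23 | 95% | 1.18 | 84% |

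**Why the gate must be applied.** At q = 0.34 and n=16 only about 47% of datasets pass. At CV 30%, coverage over all datasets is 38% (n=16) and 1% (n=50). Among those that would be reported it is 77% and 3%. At CV 50% and n=16, the two figures are 74% and 99.8%.

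**What two-thirds leaves.** At q = 0.67, CV 30% and n=50, coverage is about 36% over all datasets and about 66% among those passing the two-thirds gate.

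**Smallest permitted cell.** With values 0.5, 0.5 and 5 in LLOQ units, the geometric mean is (0.5 × 0.5 × 5)^(1/3) = 1.08, and the 95% CI runs from 0.04 to 29.

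**The case against.** The strongest objection is that the case rests on one printed fraction. The documents were machine-read, both copies of the sentence in the Amendment 3 log show two-thirds, and no amendment records a change of threshold. A misread glyph is plausible. If the source file says two-thirds, the objection to the threshold falls away and only the request for a below-LLOQ count remains. That is unproven, so the current text is judged as it reads.

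A reader might infer that the rule was silently loosened. The documents do not support that. A difference between an amendment log and the current text is not an error in itself, and Amendment 3 did not set the threshold but carried it unchanged. The log shows only that the sponsor has used two-thirds before. The fault lies in what the one-third rule permits.

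A reader might also infer that the trial's PK results will be badly biased. That does not follow either. The PK-PPS (SAP 3.4.4) requires the same dose and frequency in the feeder study and no important deviation affecting the concentration. SAP 9.1 also drops out-of-window samples and those following a non-dosing visit. Many values below LLOQ are therefore unlikely in whole-arm cells, and BMI-tertile and injection-site cells draw on the same subjects. No cell is shown to be affected.

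Finally, PK is a descriptive objective with no test, boxplots accompany the tables, and all concentrations are listed before substitution. This limits the harm. A determined reader could count the substituted values from the listings, but the summary tables would still not show them.

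**Conclusion.** The point holds at low severity. As written, SAP 9.1 allows a geometric mean, geometric CV and 95% CI to rest on up to two-thirds identical substituted values. That is arithmetic and needs no assumption. The size of the distortion depends on lognormal troughs, an assumed CV and an assumed quantifiable share. It is material at a CV of 30% with half the values quantifiable, and small at a CV of 100% with the same share. Because the documents give no LLOQ or below-LLOQ rate, the effect in this trial cannot be fixed. It is probably confined to sparse cells, such as those by ADAb status. The primary and secondary outcomes are untouched.

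**What to change.** Confirm the fraction in SAP 9.1 against the source file. If it reads one-third, change the gate to at least two-thirds of the values of interest above the LLOQ. Below that, show n, number below LLOQ, median, minimum and maximum. In either case, print the number below LLOQ in every PK summary cell. Two-thirds caps the substituted share at one-third and keeps the median a measured value, but some substitution bias remains, which is why the count is needed as well.

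The cost is one fraction in the SAP, one program threshold and one table row. The downside is that a few sparse cells lose their geometric mean and CI.
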